### **7.1.7 End of Safety Follow-Up**

The end of post-treatment phase disposition eCRF page will be completed once a subject has discontinued study treatment, completed safety follow-up.

End of post-treatment follow-up may occur one of the following reasons:

- AE
- Lost to follow-up
- Physician's decision
- Progressive disease
- Subject/guardian decision
- Death
- Protocol deviation
- Pregnancy
- Study terminated by the Sponsor
- Others

## **7.2 Assessment**

Planned time points for all safety assessments are provided in the [SoA](#).

### **7.2.1 Efficacy Assessments**

Non-Hospitalization events ([7.2.1.1](#)), NIAID ordinal scale ([7.2.1.2](#)), symptom improvement and resolution([7.2.1.3](#)) will be used to characterize the effect of GT0918 compared to placebo on clinical status from baseline to Days 14 and 28.

#### **7.2.1.1 Composite Events for non-Hospitalization**

The following events by Day 28 will be collected and recorded in the eCRF:

- Hospitalization (defined as  $\geq 24$  hours)
- Supplemental oxygen for  $\geq 24$  hours
- Death

The date of hospitalization events as above will be recorded in the eCRF. Additionally, the date for following events will also be recorded in the eCRF.

- Emergency room visit
- ICU admittance

- Discharge
- Extended care facility admittance (refers to long term care for chronic diseases or prolonged rehabilitation, which is not defined as hospitalization)

### 7.2.1.2 NIAID Ordinal Scale

The National Institute of Allergy and Infectious Diseases (NIAID) Ordinal Scale will be assessed by the site daily beginning on Day 1 through Day 28 using AE and Questionnaire data. NIAID Ordinal Scale outcomes will be analyzed on Day 7, Day 14 and Day 28.

#### NIAID Score Description

The NIAID scoring scale will be assessed daily and defined as the lowest score achieved for that day.

The scoring is based on the clinical status of the patient as described below.

1. Death
2. Hospitalized, on invasive mechanical ventilation or extracorporeal membrane oxygenation (ECMO)
3. Hospitalized, on non-invasive ventilation or high flow oxygen devices
4. Hospitalized, requiring supplemental oxygen
5. Hospitalized, not requiring supplemental oxygen - requiring ongoing medical care (COVID-19-related or other medical conditions preventing hospital discharge)
6. Hospitalized, not requiring supplemental oxygen - no longer requires ongoing medical care
7. Not hospitalized, limitation on activities and/or requiring home oxygen
8. Not hospitalized, no limitations on activities

The subjects' following conditions will be recorded in the CRF and include limitation on activities due to COVID-19:

- Ongoing hospital medical care
- Supplemental oxygen
- Non-invasive ventilation or a high flow oxygen device
- Mechanical ventilation
- ECMO

Subjects will also complete 3 questions about NAIDS as following in the patient questionnaire:

- Home oxygen
- Limited activities
- Hospitalization

### **7.2.1.3 Symptom improvement and resolution**

Subjects will rate their overall clinical status and severity of symptoms associated with COVID-19 by a daily questionnaire. This questionnaire is for outpatients only.

Subjects will complete 3 questions about their overall clinical status daily, including

- Severity of symptoms
- General physical health, and
- Change in overall health including activity limitation, home oxygen, hospitalization, etc.

The questionnaire contains these symptoms

- Cough
- Shortness of breath
- Feeling feverish
- Fatigue
- Body aches and pain
- Sore throat
- Chills
- Headache
- Nausea
- Vomiting
- Diarrhea
- Changes in taste and smell.

Each symptom will be scored daily by the subject as experienced during the past 24 hours.

Detailed list of symptoms and rating score guideline is document per Appendix 5.

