10. Laboratory tests: Hematology, Chemistry (including Creatinine Kinase), Biomarkers (including Procalcitonin, C-reactive protein, D-dimer, Ferritin, Troponin, Testosterone), Coagulation. For details refer to [Section 7.2.2](#) and [7.2.4](#).
11. GT0918 or placebo administration: GT0918 or placebo will be given orally once daily on Days 1-14 during the study period after a meal ( $\pm 2$  hours for medication scheduling). The drug taken time should be recorded with subject diary. If the screening day is also D1, the subject does not need to follow the drug taken window on screening day/D1. For details refer to [Section 6.1](#).  
Subject Diary should be completed every day since first dose until the last dose.  
Questionnaire should be completed every day since screening visit to the end of post-treatment by Day 28. For details refer to [Section 7.2.6](#).
12. Chest X-ray or CT-Scan or 12-ECG can be done per investigator's discretion. If investigator deems the result is clinically significant, the result should be recorded with eCRF.
13. Hospitalization events: if the subject is hospitalized, the treatment may be continued to the 14 days per PI. Hospitalization is defined as  $\geq 24$  hours in hospital of care. For details refer to [Section 7.1.2](#).  
Record if the following events occur:
  - Emergency room visits
  - Hospitalized
  - ICU admittance
  - Discharge
  - Extended care facility admittance (refers to long term care for chronic diseases or prolonged rehabilitation, which is not defined as hospitalization)
14. Documentation from hospital records is acceptable.  
Includes:
  - Limitation on activities due to COVID- 19
  - Ongoing hospital medical care
  - Supplemental oxygen
  - Non-invasive ventilation or high flow oxygen device
  - Mechanical ventilation
  - ECMO, or
15. Adverse events: any events that occur after signing the informed consent are considered AEs as defined in [Section 10.3](#).
16. Concomitant medications: all medications administered within 30 days prior to the first dose of study treatment through 30 days after the last dose of study treatment will be recorded in the concomitant medications, for details refer to [Section 6.4](#).
17. Pharmacokinetics (PK) samples only need to be taken for at least 100 subjects, who will be assigned according. For details refer to [Section 7.2.3](#).

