### **7.2.6 Patient Reported Outcomes**

Subjects will be provided Subject's Diary which will contain the study drug administration information (date/time, with or without meal), and the Symptoms and Overall Clinical Status Subject Questionnaire for subjects to self-evaluate their health status from their own perspective. The questionnaire is required to be completed daily, should at the same time each day (+/- 2 hours for medication scheduling), from screening to end of follow-up at Day 28. Symptoms of COVID-19 are listed per FDA guidance (<https://www.fda.gov/media/142143/download>) and the questionnaire was modified based on this FDA guidance as well, referred to Appendix 5.

The Sponsor and investigators will make efforts to minimize the amount of missing data, include providing reminders (e.g., phone calls, text messages, email) to study subjects to complete Patient Reported Outcomes (PRO) instruments, monitoring compliance with PRO instrument completion throughout the assessment period, following up with study subjects who are not successfully completing PRO instruments (and, where permissible, close contacts if the study subject is not responding), and recording verbal responses for those who are unable to self-record because of illness or other circumstances. Sponsor and investigators/ sites will try to obtain contact information for close contacts of study subjects for use in case of nonresponse. This such close contacts include family member (s) or other close contact when subjects do not respond to follow-up, this process is described in the informed consent document, will be (is) approved by the institutional review board and agreed with subjects. The reasons for missing data should be documented with subject's CRF.

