**NIAID Daily Questions**

1. In the past 24 hours, have you been hospitalized?

Yes	No
	

2. In the past 24 hours, have you required home oxygen?

Yes	No
	

3. In the past 24 hours, have you had any limitation on your activities?

Yes	No
	

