Continuous data will be summarized in terms of the mean, standard deviation (SD), median, minimum, maximum, and number of observations, unless otherwise stated. Continuous data that are expected to be skewed will be presented in terms of the maximum, upper quartile, median, lower quartile, minimum and number of observations. The minimum and maximum will be reported to the same number of decimal places as the raw data recorded in the database. The mean, median, lower quartile and upper quartile will be reported to one more decimal place than the raw data recorded in the database. The SD will be reported to two more decimal places than the raw data recorded in the database. In general, the maximum number of decimal places reported shall be four for any summary statistic.

Categorical data will be summarized in terms of the number of subjects providing data at the relevant time point (n), frequency counts and percentages. Any planned collapsing of categories will be detailed in the SAP text and the data displays.

Percentages will be presented to one decimal place. Percentages will not be presented for zero counts. Percentages will be calculated using n as the denominator. If sample sizes are small, the data displays will show the percentages, but any textual report will describe frequencies only.

Changes from baseline in categorical data will be summarized using shift tables where appropriate.

P-values greater than or equal to 0.0001, in general, will be presented to four decimal places. P-values less than 0.0001 will be presented as “<0.0001” and p-values greater than 0.9999 will be presented as “>0.9999”.

Confidence intervals will be presented to one more decimal place than the raw data.

Analysis Visit Window:

For unscheduled visits, analysis visit windows will be applied as in [Table](#) below. Analysis visit windows are only used for by visit summaries, not for time to event calculation which will be based on actual date of data collected.

Table 1 Analysis Visit Window for Unscheduled Visits of blood samples

Mapped to	Visit Window
Screening	[Day -1, Day 1]
Day 3	[Day 2, Day 4]
Day 7	[Day 6, Day 8]
Day 14	[Day 13, Day 15]
Day 28	[Day 26, Day 30]
Day 42	[Day 40, Day 44]

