
All hospitalization events and COVID-19 related medical attended visits will be listed.

Time to Hospitalization

Time to Hospitalization (in days) is defined as:

First hospital admission date - first dosing date + 1.

Note: Hospitalization (≥ 24 hours) includes Hospitalization, Emergency room and ICU. Extended Care Facility Admittance is excluded.

The following two summaries will be generated separately:

- All-Cause Hospitalization
- COVID-19 Related Hospitalization

If a patient has not experienced hospitalization by completion or early discontinuation of study/study treatment, the patient will be censored at the date of their last visit during the post-treatment period.

Time to hospitalization will be evaluated up to Day 28 and will be summarized and plotted by treatment group with mITT set using the Kaplan-Meier (KM) method. The 2-sided 95% CIs for the 25th, 50th and 75th percentiles, as well as at days 3, 7, 14 and 28 using the Brookmeyer and Crowley method will be reported when estimable. P-value will be obtained from the log-rank test stratified by age, and sex, race and ethnicity, and number of risk factors at randomization. Hazard ratios and corresponding 95% confidence intervals will be obtained from a Cox proportional hazard model which treated treatment group as a unique covariate, and age, and sex, race and ethnicity, and number of risk factors as stratas. The Cox proportional hazard model will be also performed by subgroup of duration since symptom onset to randomization category (≤ 3 days; > 3 days).

If cases of hospitalization are too sparse (e.g., < 1 case in one treatment group), no time to hospitalization analyses will be performed.

Proportion of Symptom Resolution

All symptom resolution is defined as

all symptoms (those scored 0-3*) on the symptom questionnaire scored as absent (scored 0), with each symptom resolution absent for at least 48 hours.

Note: * Seven individual questions from COVID-19-Related Symptom Questionnaire are included here: questions 3, 4, 5, 6, 7, 8 and 9.

Additionally, all symptom resolution will be defined differently to include all individual questions scored 0-3 and related outputs will be noted as sensitivity analysis. It is defined as

all symptoms (those scored 0-3*) on the symptom questionnaire scored as absent (scored 0), with each symptom resolution absent for at least 48 hours.

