Note: * Nine individual questions from COVID-19-Related Symptom Questionnaire are included here: questions 1 through 9.

The proportion of subjects with all symptom resolution will be performed at Days 3, 7, 14, and 28 by treatment in frequency tables and listed using mITT set. Generalized estimating equation (GEE) model will be fitted with the response of symptom resolution mapped to categories of Yes or No and with treatment, age, stratification factors (sex, race and ethnicity, and number of risk factors), time

effect and time*treatment interaction terms included in the model as covariates. Odds ratios with 95% confidence intervals and p-values will be present.

Total symptom score (seven individual questions from COVID-19-Related Symptom Questionnaire included here are questions 3, 4, 5, 6, 7, 8 and 9) and change from baseline in total symptom score to Days 3, 7, 11, 14 and 28 will be summarized by treatment group. Change from baseline will be compared using mixed model repeated measures (MMRM) with the fixed effects of baseline total symptom score, age and stratification factors (sex, race and ethnicity, and number of risk factors) and the random effect of subjects and with time effect and time*treatment interaction terms included in the model. Change from baseline in total symptom score will also be graphically displayed.

Additionally, total symptom score will be calculated differently to include nine individual questions (1 through 9) and related outputs will be noted as sensitivity analysis.

A summary of overall COVID-19 related symptoms, including overall symptoms severity, overall general physical health and returned to usual physical health, at Days 3, 7, 11, 14 and 28 will be provided in frequency table and listed.

Additionally, the proportion of subjects with at least 2 points decrease in symptom score (total of ratings) from baseline to Days 3, 7, 14 and 28 will be summarized and listed as well. Generalized estimating equation (GEE) model will be fitted with the response of at least 2 points decrease mapped to categories of Yes or No and with treatment, age, stratification factors (sex, race and ethnicity, and number of risk factors), time effect and time*treatment interaction terms included in the model as covariates. Odds ratios with 95% confidence intervals and p-values will be present.

Time to All Symptom Resolution

Time to all symptom resolution (in days) is defined as:

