First date when all symptom resolution status is changed to 'Yes' - first dosing date + 1.

If a patient has not experienced symptom resolution by completion or early discontinuation of study/study treatment, the patient will be censored at the date of their last visit during the post-treatment period.

Time to all symptom resolution will be applying the same KM methods and Cox proportional hazard models introduced in the time to hospitalization section.

Symptom Improvement

Symptom improvement is defined as a change in severity of overall symptoms * from a higher score to a lower score, which is defined as following:

symptoms scored as moderate or severe at baseline are scored as mild or absent,
OR

symptoms scored as mild or absent at baseline are scored as absent.

Note: * The overall symptoms question (overall question 1) under overall COVID-19 related symptoms from COVID-19-Related Symptom Questionnaire is included here.

Additionally, symptom improvement will be defined by individual symptom questions from symptom questionnaire as below and related outputs will be noted as sensitivity analysis. It is defined as a patient experiencing both:

symptoms * scored as moderate or severe at baseline are subsequently scored as mild or absent,

AND

symptoms * scored as mild or absent at baseline are subsequently scored as absent.

Note: * Seven individual questions from COVID-19-Related Symptom Questionnaire are included here: questions 3, 4, 5, 6, 7, 8 and 9.

The proportion of subjects with symptom improvement at Days 3, 7, 11, 14 and 28 will be summarized by treatment in frequency tables and listed using mITT set. Generalized estimating equation (GEE) model is fitted with the response of symptom improvement mapped to categories of Yes or No and with treatment, age, stratification factors (sex, race and ethnicity, and number of risk factors), time effect and time*treatment interaction terms included in the model as covariates. Odds ratios with 95% confidence intervals and p-values will be present.

Time to Symptom Improvement

Time to symptom improvement (in days) is defined as:

Date when symptom improvement status is changed to 'Yes' - first dosing date + 1.

If a patient has not experienced symptom improvement by completion or early discontinuation of study/study treatment, the patient will be censored at the date of their last visit during the post-treatment period.

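### By-visit symptom results leave out subjects in hospital or dead on the visit day, and the time-to-event results censor deaths as if recovery were still possible

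*Protocol*

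**What the plan says.** **Collection.** Protocol 7.2.1.3: "This questionnaire is for outpatients only". Other places read differently. Annotation 11 to the Schedule of Activities says: "Questionnaire should be completed every day since screening visit to the end of post-treatment by Day 28". Protocol 7.1.5 repeats daily collection to Day 28. Protocol 7.2.6 provides for "recording verbal responses for those who are unable to self-record because of illness or other circumstances". The questionnaire in Appendix 5 asks: "In the past 24 hours, have you been hospitalized". None of these mentions inpatients as an exception or as included.

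**Endpoint definitions.** SAP 4.10.3 defines all symptom resolution as all counted symptoms "on the symptom questionnaire scored as absent (scored 0), with each symptom resolution absent for at least 48 hours". Symptom improvement is likewise a change in questionnaire scores. Neither definition requires the subject to be alive or out of hospital.

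**By-visit analysis.** SAP 4.2 takes subjects with data at the time point as the denominator for percentages. For resolution, SAP 4.10.3 says: "Generalized estimating equation (GEE) model will be fitted with the response of symptom resolution mapped to categories of Yes or No". Improvement is modelled in the same way. Nothing says what to do when there is no questionnaire.

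**Time to resolution and time to improvement.** For a subject without the event, SAP 4.10.3 says "the patient will be censored at the date of their last visit" within the post-treatment period, which SAP 4.11 runs from the day after the last dose to Day 28. Death has no separate rule. Protocol 10.5.2.4 and 10.5.2.6 name the treatment period instead, but Protocol 10.1 gives the SAP precedence.

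**Missing data.** Protocol 10.5.1.3 leaves further detail to the SAP. The SAP's missing-outcome rule (4.10.1.1.1) and its list of intercurrent events (4.10.2) concern the primary endpoint only.

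**The concern.** Hospitalization and death are components of the primary endpoint. If the symptom record is absent because a subject is in hospital or dead, missingness depends on the outcome the drug is meant to change. The by-visit comparison is then between those well enough to answer in each arm.

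The direction depends on the treatment effect. If GT0918 prevents hospitalization, placebo loses more of its sickest subjects, its resolution rate looks better than it is, and benefit is hidden. If GT0918 causes harm, the bias hides that harm.

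For time to event, censoring a death at the last visit assumes the subject had the same later chance of recovery as those still followed. That chance was zero.

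These analyses produce odds ratios, hazard ratios and p-values that will be read as separate secondary results.

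**Working it through.** **1. The plan's own figure.** The documents give no figure for the symptom endpoints. The planning rates used below come from the sample size statement (Protocol 10.9, SAP 4.12): 97% vs 91% event-free, 668 subjects, one-sided 0.025, one interim at 50% information, about 90% power. That statement reproduces:

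- O'Brien-Fleming-type spending at half information gives an interim p of 0.0015 and a final p of 0.0245.
- With 334 per arm and unpooled variance 0.97×0.03 + 0.91×0.09 = 0.111, the drift is 0.06/√(0.111/334) = 3.29 and power is 90.8%.
- With pooled variance 2×0.94×0.06 = 0.1128, power is 90.3%.

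The figure is not in dispute.

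**2. What happens to one subject.**

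| Status | By-visit tables and GEE | Time to event |
|---|---|---|
| In hospital on the visit day, later attends Day 28 unresolved | No record under 7.2.1.3, so not in numerator or denominator at that visit; may return after discharge | At risk to about Day 28 |
| Dead, with a visit in the post-treatment period | Absent from every visit after death | Censored at that visit |
| Dead before the post-treatment period | Absent from every visit after death | No such visit exists; rule undefined |

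A GEE fitted without a fill-in rule uses the records available, so it inherits the omission.

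**3. Size.** Let *r* be the resolution proportion among subjects with data, assumed equal in both arms, and let *e* be the proportion of an arm absent because of hospitalization or death.

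- Omitting these subjects: *r* in each arm, difference 0.
- Counting them as not resolved: *r*(1 − *e*), so the difference (GT0918 minus placebo) is *r*(*e*_placebo − *e*_GT0918).

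Planning rates, 9% vs 3% (334×0.09 ≈ 30 and 334×0.03 ≈ 10 subjects), with *r* = 60% assumed:

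- placebo 0.60×0.91 = 54.6%; GT0918 0.60×0.97 = 58.2%; difference 3.6 points
- odds ratio (0.582/0.418)/(0.546/0.454) = 1.16

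Assumed 3% vs 1%, averaging 2%, chosen because SAP 4.10.1.1.3 reports under 2% hospitalization:

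- placebo 0.60×0.97 = 58.2%; GT0918 0.60×0.99 = 59.4%; difference 1.2 points
- odds ratio (0.594/0.406)/(0.582/0.418) = 1.05

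Since *r* is not in the documents, the range is:

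| Assumed *r* | 9% vs 3% | 3% vs 1% |
|---|---|---|
| 30% | 1.8 points | 0.6 points |
| 50% | 3.0 | 1.0 |
| 60% | 3.6 | 1.2 |
| 70% | 4.2 | 1.4 |
| 90% | 5.4 | 1.8 |

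With equal event rates in the two arms the difference is 0 for any *r*.

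**4. Why each entry is a ceiling for its *r*.** The rates are cumulative to Day 28, whereas the omission affects only those in hospital or dead on the visit day. The composite also includes supplemental oxygen given outside hospital (Protocol 2.2), and those subjects are still outpatients who can answer.

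**5. Against sampling error.** With *r* = 60% and 334 per arm, the standard error of the difference is √(2×0.6×0.4/334) = 3.8 points. The ceilings are 3.6/3.8 ≈ 0.95 and 1.2/3.8 ≈ 0.3 standard errors.

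**The case against.** **The documents do not clearly rule out inpatient records.** Daily completion to Day 28, verbal responses for those too ill to write, and a hospitalization item all point the other way. This stands as far as it goes: a reader might infer that no hospitalized subject will ever have a record, and the text does not establish that. But these provisions do not override the outpatient restriction, the hospitalization item can be answered after discharge, and none of them covers a death or says how to score an absent record.

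**Hospitalized subjects are not lost from every symptom analysis.** Correct. A reader might conclude that the worst outcomes also drop out of time to resolution and time to improvement. They do not: the Kaplan-Meier and Cox methods carried over from the time-to-hospitalization section use the mITT set, and a hospitalized survivor seen unresolved at Day 28 remains at risk. Only deaths are mishandled there.

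**The severe outcomes are captured elsewhere.** They enter the primary endpoint, the hospitalization percentage, the NIAID scale and, for hospitalization, time to hospitalization. So efficacy as a whole does not lose them. That does not correct the symptom odds ratios and hazard ratios.

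**Counting hospitalization as not resolved is an estimand choice.** It is a composite strategy, it would also count a non-COVID admission, and it partly repeats the primary endpoint. That is fair. But the plan has not chosen any alternative for these endpoints; the present handling arises from the denominator and censoring rules.

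**Events are rare.** This limits the size of the bias but does not supply the missing rule.

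**Conclusion.** The gap is real and small. As written, the by-visit resolution and improvement results omit subjects in hospital or dead on the visit day and so favour the arm with more of them. The time-to-event results treat deaths as still able to recover, and give no usable rule for a death before the post-treatment period.

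The 3.6 points at planning rates should not be read as the expected bias. It rests on an assumed 60% resolution, equal among responders in both arms, and on every composite event being absent on the same day. With the under-2% hospitalization the SAP reports, about 1.2 points is the more relevant ceiling at that assumption. The SAP figure is not split by arm, so the 3% vs 1% division is also an assumption. Nor do the documents show which arm gains, since that depends on event rates they do not give by arm.

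The point concerns secondary endpoints and leaves the primary analysis and the sample size untouched. It is worth correcting because correction is easy, not because it threatens the trial's main conclusion.

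**What to change.** In SAP 4.10.3:

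1. **By-visit resolution and improvement (tables and GEE).** Count a subject who is hospitalized or dead on the visit day as not resolved and not improved, and keep that subject in the mITT denominator.
2. **Time to resolution and time to improvement.** Keep deaths in the risk set without the event and censor them at Day 28. This also resolves the undefined case.
3. **Collection text.** Reconcile the outpatient restriction in Protocol 7.2.1.3 with annotation 11 to the Schedule of Activities, 7.1.5 and 7.2.6, so that it is clear whether inpatient responses are collected and used.

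The MMRM of change in total symptom score is not repaired by these rules, because a not-resolved status supplies no score. Its handling of hospitalized and dead subjects needs a separate statement.

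Cost: two derivation rules and a wording clarification. Hospitalization, death and discharge dates are recorded under Protocol 7.2.1.1, and daily NIAID status to Day 28 under 7.2.1.2. No new data, visits or subjects are needed. The rules should be fixed before treatment codes are opened.
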